5.7.2 Instructions for initiation of a New Cycle

A new course of treatment may begin on the scheduled Day 1 of a new cycle if::

- The ANC is $\geq 1500/\text{mm}^3$;
- The platelet count is $100,000 \geq /\text{mm}^3$; (If held during the previous cycle for low platelet count, prophylactic anti-coagulation should be re-started when platelet count is $\geq 75,000$)
- Any drug-related rash or neuropathy that may have occurred has resolved to \leq grade 1 severity;
- Any other drug-related adverse events that may have occurred have resolved to \leq grade 2 severity.

If these conditions are not met on Day 1 of a new cycle, the subject will be evaluated weekly and a new cycle of treatment will not be initiated until the toxicity has resolved as described above. If a lenalidomide or everolimus dose reduction was taken during the previous cycle, and the cycle was completed without requiring further dose modification, then the next cycle will start at the same reduced dose. **If drug dosing was omitted for the remainder of the previous cycle or if the new cycle is delayed due to toxicity newly encountered on the scheduled Day 1**, then the

new cycle will be started with a one-level dose reduction of the drug to which the toxicity was attributed.

5.7.3 Instructions for dose modifications or interruption during a cycle

This information is meant to assist in dose modification for individual study participant who experienced a treatment-related toxicity. The dose escalation schema for the study cohort will proceed as described under the escalation schema (refer Table 1, Section 5.1).

In the event of treatment interruption due to study-drug related toxicity, both agents will be held until the patient is able to resume further therapy. At the time of dosing resumption, alternate dose reduction strategy will be employed if the dose reduction is necessitated by hematologic toxicity. This alternate dose reduction will always start with Lenalidomide (not required if already at the minimum dose of 5mg) followed by Everolimus if further reduction is still necessary. In the case of non-hematological toxicity, dose reduction will be limited to the drug with the highest likelihood of attribution. In case of equal likelihood of attribution or where clear attribution is impossible, simultaneous reduction of both drugs will be effected at resumption of therapy.

NB: Patients unable to resume treatment within the allotted time period for recovery from treatment-related toxicities detailed in Table 5 and Table 6 may be allowed to resume treatment with express approval of the study sponsor provided they have evidence of clinical benefit from treatment and the toxicity has resolved to a level considered safe for further treatment with everolimus or lenalidomide. Also, patient may be allowed to continue on only one study drug if a permanent discontinuation of the other study drug is mandated by a unique treatment-related toxicity e.g. discontinuation of lenalidomide for desquamating rash.

Table 5: Dose Modifications NOTE: Please consider altering threshold hematologic toxicity criteria for dose modifications depending on specific disease and patient population involved in study, and with consideration given to the Inclusion Criteria and the Instructions for Initiation of a New Cycle. Also consider whether the use of G-CSF is permitted as outlined in the neutropenia row. For combination therapy trials, please consider the following recommendations/issues: 1) it is highly recommended that appropriate dose modifications (holding and reductions as needed) for other drugs in the regimen are incorporated into this table, 2) whether the holding of 1 drug requires other drugs to be held, 3) for drugs with overlapping toxicities (hematologic toxicities, for example) please consider, if appropriate, alternating dose reductions by episode (reduce 1 drug for the first episode and then another drug for the second episode and continuing to alternate which drug is reduced for subsequent reductions as needed, and 4) whether dose modifications for the category "other non-hematologic toxicities \geq grade 3" should be based on attribution (this is recommended).

NCI CTC Toxicity Grade	Dose Modification Instructions
Grade 3 neutropenia associated with fever (temperature \geq 38.5° C) or Grade 4 neutropenia	
 • Hold (interrupt) lenalidomide dose. • Follow CBC weekly. • If neutropenia has resolved to \leq grade 2 within 14 days, restart lenalidomide at next lower dose level and continue through the scheduled end of the cycle. Otherwise, omit for remainder of cycle and reduce the dose of lenalidomide by 1 dose level at the start of the next cycle. Omitted doses are not made up. If neutropenia is the only toxicity for which a dose reduction is required, G-CSF may be used and the lenalidomide dose maintained prior to considering dose reduction for Everolimus.
Thrombocytopenia \geq Grade 3 (platelet count $<$ 50,000/mm³)	
 • Hold (interrupt) lenalidomide dose. • Follow CBC weekly. • If thrombocytopenia resolves to \leq grade 2 prior to Day 21 of the current cycle, restart lenalidomide at next lower dose level and continue through the scheduled Day 21 of the current cycle. Otherwise, omit for remainder of cycle and reduce the dose of lenalidomide by 1 dose level at the start of the next cycle. Omitted doses are not made up.
Platelet count $<$ 50,000/mm³	
 • Hold prophylactic anti-coagulation, if applicable. • Restart prophylactic anti-coagulation when platelet count is \geq 75,000/mm³.
Non-blistering rash Grade 3 Grade 4	
 • If Grade 3, hold (interrupt) lenalidomide dose. Follow weekly. • If the toxicity resolves to \leq grade 1 prior to Day 28, restart lenalidomide at next lower dose level and continue through the scheduled end of the cycle. Otherwise, omit for remainder of cycle and reduce the dose of lenalidomide by 1 dose level at the start of the next cycle. Omitted doses are not made up. • If Grade 4, discontinue lenalidomide. Remove patient from study.
Desquamating (blistering) rash- any Grade	
 • Discontinue lenalidomide. Remove patient from study.

Table 5: Dose Modifications NOTE: Please consider altering threshold hematologic toxicity criteria for dose modifications depending on specific disease and patient population involved in study, and with consideration given to the Inclusion Criteria and the Instructions for Initiation of a New Cycle. Also consider whether the use of G-CSF is permitted as outlined in the neutropenia row. For combination therapy trials, please consider the following recommendations/issues: 1) it is highly recommended that appropriate dose modifications (holding and reductions as needed) for other drugs in the regimen are incorporated into this table, 2) whether the holding of 1 drug requires other drugs to be held, 3) for drugs with overlapping toxicities (hematologic toxicities, for example) please consider, if appropriate, alternating dose reductions by episode (reduce 1 drug for the first episode and then another drug for the second episode and continuing to alternate which drug is reduced for subsequent reductions as needed, and 4) whether dose modifications for the category "other non-hematologic toxicities \geq grade 3" should be based on attribution (this is recommended).
	
NCI CTC Toxicity Grade	Dose Modification Instructions

Neuropathy
 
Grade 3
 
Grade 4
	
 If Grade 3, hold (interrupt) lenalidomide dose. Follow at least weekly. If the toxicity resolves to \leq grade 1 prior to Day 28, restart lenalidomide at next lower dose level and continue through the scheduled end of the cycle. Otherwise, omit for remainder of cycle and reduce the dose of lenalidomide by 1 dose level at the start of the next cycle. Omitted doses are not made up. If Grade 4, discontinue lenalidomide. Remove patient from study.

Venous thrombosis/embolism \geq Grade 3
	
 Hold (interrupt) lenalidomide and start anticoagulation; restart lenalidomide at investigator's discretion (maintain dose level). Omit lenalidomide for remainder of cycle. See Anticoagulation Consideration (Section 5.7.2)

Hyperthyroidism or hypothyroidism
	
 Omit lenalidomide for remainder of cycle, evaluate etiology, and initiate appropriate therapy. Resume lenalidomide at the same dose for 1st occurrence Reduce dose of lenalidomide with 2nd occurrence See Instructions for Initiation of a New Cycle

other non-hematologic toxicity \geq Grade 3
	
 Hold (interrupt) lenalidomide dose. Follow at least weekly. If the toxicity resolves to \leq grade 2 prior to Day 28, restart lenalidomide and continue through the scheduled end of the cycle. Otherwise, omit for remainder of cycle. Omitted doses are not made up. For toxicity attributed to lenalidomide, reduce the lenalidomide dose by 1 dose level when restarting lenalidomide.

Table 6: Dose Interruption/Modification Guidelines for Everolimus

Please note that in case of hematological toxicity, Everolimus dose reduction should be considered only if the dose reduction for lenalidomide has been effected as per Table 5 above and found to be ineffective or insufficient to allow the patient to safely resume therapy per protocol guidelines

Toxicity	Actions

Non-hematological toxicity
 
Grade 2 (except pneumonitis – refer to Table 3-2)
 
Grade 3 (except hyperlipidemia*) (except pneumonitis – refer to Table 3-2)
 
Grade 4
	
If the toxicity is tolerable to the patient, maintain the same dose. If the toxicity is intolerable to patient, interrupt RAD001 until recovery to grade ≤ 1. Then reintroduce RAD001 at same dose. If event returns to grade 2, then interrupt RAD001 until recovery to grade ≤ 1. Then reintroduce RAD001 at the lower dose level.
 
Interrupt RAD001 until recovery to grade ≤ 1. Then reintroduce RAD001 at the lower dose level. For pneumonitis consider the use of a short course of corticosteroids.
 
Discontinue RAD001.


Hematological toxicity
 
Grade 2 Thrombocytopenia (platelets <75, $\geq 50 \times 10^9/L$)
 
Grade 3 Thrombocytopenia (platelets <50, $\geq 25 \times 10^9/L$)
 
Grade 4 Thrombocytopenia (platelets $< 25 \times 10^9/L$)
 
Grade 3 Neutropenia (neutrophils <1, $\geq 0.5 \times 10^9/L$)
 
Grade 4 Neutropenia (neutrophils $< 0.5 \times 10^9/L$)
 
Grade 3 febrile neutropenia (not life-threatening)
 
Grade 4 febrile neutropenia (life-threatening)
	
Interrupt RAD001 until recovery to grade ≤ 1 ($>75 \times 10^9/L$). Then reintroduce RAD001 at initial dose. If thrombocytopenia again returns to grade 2, interrupt RAD001 until recovery to grade ≤ 1. Then reintroduce RAD001 at the lower dose level.
 
Interrupt RAD001 until recovery to grade ≤ 1 (platelets $\geq 75 \times 10^9/L$). Then resume RAD001 at one dose level lower. If grade 3 thrombocytopenia recurs, discontinue RAD001.
 
Discontinue RAD001.
 
Interrupt RAD001 until recovery to grade ≤ 1 (neutrophils $\geq 1.5 \times 10^9/L$). Then resume RAD001 at the initial dose. If ANC again returns to Grade 3, hold RAD001 until the ANC $\geq 1.5 \times 10^9/L$. Then resume RAD001 dosing at the lower dose level. Discontinue patient from study therapy for a third episode of grade 3 neutropenia.
 
Interrupt RAD001 until recovery to grade ≤ 1 (neutrophils $\geq 1.5 \times 10^9/L$). Then resume RAD001 at the lower dose level. If grade 3 or grade 4 neutropenia occurs despite this dose reduction, discontinue RAD001.
 
Interrupt RAD001 until resolution of fever and neutropenia to grade ≤ 1. Hold further RAD001 until the ANC $\geq 1,500/mm^3$ and fever has resolved. Then resume RAD001 at the lower dose level. If febrile neutropenia recurs, discontinue RAD001.
 
Discontinue RAD001.

Any hematological or non-hematological toxicity requiring interruption for ≥ 3 weeks
	
Discontinue RAD001

Grade 3 hyperlipidemia (hypercholesterolemia and/or hypertriglyceridemia) should be managed using medical therapies (see Sec. 3.2.5.2).

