5.7.4 Monitoring of RAD001 suspected toxicities

Patients whose treatment is interrupted or permanently discontinued due to an adverse event or abnormal laboratory value suspected to be related to RAD001 must be followed at least weekly until the adverse event or abnormal laboratory resolves or returns to grade 1. If a patient requires a dose delay of > 21 days from the intended day of the next scheduled dose, then the patient must be discontinued from the study.

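### Section 5.7.3 holds both drugs together but sets no recovery level; Tables 5 and 6 disagree on when to hold and restart, and the maximum-delay rules differ in consequence

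*Combined protocol and SAP*

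**What the plan says.** Four parts of section 5.7 apply to the same patient.

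- **Section 5.7.3, general rule.** When treatment is interrupted for drug-related toxicity, "both agents will be held until the patient is able to resume further therapy". What makes a patient able to resume is not defined there.
- **Table 5 (lenalidomide).** The instruction in the cytopenia rows is "Hold (interrupt) lenalidomide dose". The neutropenia row begins at "Grade 3 neutropenia associated with fever" or grade 4, and the platelet row at grade 3. Restart is allowed at grade 2 or lower, within 14 days for neutropenia and before Day 21 for platelets. The table still carries a template note asking the author to consider "whether the holding of 1 drug requires other drugs to be held".
- **Table 6 (everolimus).** Interruption begins at grade 2 thrombocytopenia and at "Grade 3 Neutropenia (neutrophils <1" x10^9/L, down to 0.5), with no fever required. Where resumption is allowed, recovery to grade 1 or lower is needed. Its last row, "Any hematological or non-hematological toxicity requiring interruption for" 3 weeks or longer, discontinues everolimus.
- **Section 5.7.4.** If a dose is delayed more than 21 days past the intended day, "then the patient must be discontinued from the study".

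The note in 5.7.3 adds that patients who exceed the recovery times in Tables 5 and 6 "may be allowed to resume treatment with express approval of the study sponsor", subject to evidence of clinical benefit and adequate resolution of the toxicity. It names those two tables only.

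**The concern.** Different thresholds for two drugs are no problem if each drug is managed separately. Here the general rule ties them together and then leaves the trigger and recovery levels to tables that give different answers. An investigator who follows one table restarts a drug that the joint hold may still be withholding. One who follows the other keeps both drugs off for longer. Once a delay passes 21 days, the same patient may lose one drug, leave the study, or resume, depending on which paragraph is read.

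Three things are at stake: continued exposure to study drug during an unresolved toxicity, the dose intensity reported for each dose level, and which patients are still on treatment at the response assessments made after every two cycles.

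**Working it through.** No figure in the plan has to be reproduced; this is a comparison of texts. The grade limits are those printed in Table 6, in x10^9/L. For platelets, grade 2 is 50 to below 75, grade 3 is 25 to below 50, and grade 1 or lower is 75 and above. For neutrophils, grade 3 is 0.5 to below 1.0, grade 4 is below 0.5, and grade 1 or lower is 1.5 and above. That leaves 1.0 to below 1.5 as grade 2.

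**Step 1: resumption within a cycle**

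| Situation | Table 5, lenalidomide | Table 6, everolimus | Section 5.7.3 |
|---|---|---|---|
| Neutrophils 1.0–1.49 after grade 4 neutropenia, within 14 days | Restart level met | Withhold; 1.5 needed | Joint hold; end point not stated |
| Platelets 50–74 after grade 3 thrombocytopenia, before Day 21 | Restart level met | Withhold; 75 needed | Joint hold; end point not stated |

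In both rows the disagreement spans the whole of grade 2. If the joint hold stands, Table 5's restart cannot be carried out. If Table 5 is followed, the hold is no longer joint.

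**Step 2: trigger**

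| Situation | Table 5 | Table 6 |
|---|---|---|
| Platelets 50–74, new | No hold triggered | Interrupt |
| Neutrophils 0.5–0.99, no fever | No hold triggered | Interrupt |

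Once Table 6 causes an interruption, 5.7.3 can be read as extending it to lenalidomide. The open question is again how the hold ends. At platelets of 60, Table 5's restart level (50 or above) is already met on the day the hold begins, while Table 6's level (75) is not.

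**Step 3: new cycle.** Section 5.7.2 sets a single requirement for starting a new cycle: neutrophils of at least 1500/mm³ and platelets of at least 100,000/mm³. It does not govern a restart within a cycle, and it states no maximum delay.

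**Step 4: maximum delay.** Three weeks is 3 x 7 = 21 days.

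| Delay | Table 6 | Section 5.7.4 | Note in 5.7.3 |
|---|---|---|---|
| 20 days | Limit not reached | Limit not reached | Not needed for this limit |
| 21 days | Everolimus ends | Limit not reached | Resumption possible with approval |
| 22 days | Everolimus ends | Study participation ends | Resumption possible with approval, but 5.7.4 not named |

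The numerical limits differ only at day 21. The consequences differ at every longer delay: loss of one drug, loss of study participation, or possible resumption.

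**The case against.** The best defence is that the instructions are cumulative. Table 5 never says to continue everolimus and Table 6 never says to continue lenalidomide. Section 5.7.3 is the combination rule, and it answers the template question left in Table 5. The note is a deliberate exception, and the list of changes records a clarification on delayed recovery. Much of this stands. It settles which drugs are held, but not which recovery level releases them, and it does not extend the exception to the mandatory wording of 5.7.4. The lenalidomide-first order in 5.7.3 and before Table 6 concerns dose reductions, not the length of a hold.

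Several stronger readings are tempting, and the documents do not support them.

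- A reader might infer that platelets of 60 produce three incompatible instructions. Section 5.7.3 is not an independent trigger. Table 6 can start the interruption and 5.7.3 extend it, which is one outcome.
- A reader might infer that cycle-1 doses missed for cytopenia count as DLTs. The synopsis and section 4.2.1 limit that criterion to unexpected toxicity. Cytopenias are listed among lenalidomide's frequent events, and the package inserts that define what is expected are not in the documents.
- A reader might turn instead to the DLT criterion on failure to re-treat within 2 weeks. If that refers to the next cycle, 5.7.2 governs with one set of levels. The point does not rest on it.
- A reader might assume that cytopenias are the main toxicity of the combination. Section 5.7.5 names grade 3 stomatitis as the principal everolimus DLT in phase 1, and the lenalidomide myelosuppression described in section 5.2.2 comes from myeloma.
- The limits in Table 7 are specific to pneumonitis and do not contradict the general limits.

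**Conclusion.** The point holds as an internal inconsistency that should be resolved. For recovery in the grade 2 range after grade 4 neutropenia or grade 3 thrombocytopenia, the joint hold, Table 5's restart and Table 6's continued withholding cannot all be followed. For delays beyond 21 days, the stated consequences cannot all apply, and no order of precedence is given.

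The extent is known in terms of laboratory values and days, not patients. The documents give no rate of these events for the combination, so no effect on dose intensity or response can be calculated. For scale only, one patient is 1/15 = 6.7 percentage points of the 15-patient expansion cohort and 1/9 = 11.1 points of the adenoid cystic cohort, where section 10.6 looks for at least 3 responses in 9. The conclusion assumes that section 5.7.3 means what it says about holding both drugs. If the drugs were meant to be managed independently, different thresholds would not conflict, but that sentence would then be wrong.

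**What to change.** Reconcile section 5.7.3, section 5.7.4, Table 5 and Table 6, so that the text states:

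1. the order of precedence between the combination rule and the single-drug tables;
2. which table's trigger starts the joint hold and which recovery level ends it;
3. whether the exception in the 5.7.3 note applies to the limit in 5.7.4;
4. whether exceeding the delay limit ends one drug or study participation.

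Remove the template note above Table 5 once these are settled. The thresholds and rules, including whether the two drugs should share one, are for the sponsor; none is proposed here. The cost is a text amendment to the dose-modification section, with no change to sample size or analysis.

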Discrete, reversible changes in liver enzymes have been found to occur in numerous patients during treatment with RAD001 in oncology clinical studies, and in a study in rheumatoid arthritis. In oncology studies, these changes may be evident only in patients without severe underlying morbidity. The increase in transaminase's (AST and ALT) generally appears after 4 weeks of treatment. In all but a few cases it does not exceed Grade 1 ($\leq 2.5 \times \text{ULN}$). Similarly, mild increases in alkaline phosphatases can coexist. Spontaneous corrections or intermittent correction with continued treatment can occur. Serum bilirubin is not increased. In studies of patients with advanced cancers, clinically relevant changes in liver enzymes have been invariably associated with the presence of liver metastases and/or progression of the underlying cancer.

Renal failure has been reported in five suspected cases to date. One patient with no alternative explanation made a complete recovery following study drug adjustment and no treatment/therapy for the event. The rest of the patients had concurrent morbidities, which might have contributed to the reported events.

Hypophosphatemia, hypomagnesemia, hyponatremia and hypocalcemia have been reported as serious adverse reactions. Electrolytes should be monitored in patients treated with RAD001.

Table 6 provides general recommendations for the management of patients, with suspected drug toxicities while on treatment with RAD001 as single-agent therapy.

More detailed information regarding RAD001 reported suspected toxicities and individual cases is provided in the [Investigator's Brochure].

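### The protocol puts lenalidomide reduction first after hematologic toxicity, but the Grade 4 discontinuation rows of Table 6, Section 5.7.2 and the G-CSF sentence in Table 5 do not fit that order

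*Combined protocol and SAP*

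**What the plan says.** Section 5.7.3 holds both drugs when treatment is interrupted for drug-related toxicity. For hematologic toxicity it then fixes the order of reduction on resumption: "This alternate dose reduction will always start with Lenalidomide", unless that drug is already at its 5 mg minimum, and everolimus comes next if more is needed. Two other places carry the same order:

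- The main text of the Table 5 neutropenia and thrombocytopenia rows names lenalidomide as the drug to step down.
- The note heading Table 6 says that in hematologic toxicity "Everolimus dose reduction should be considered only if the dose reduction for lenalidomide has been effected as per Table 5" and has proved ineffective or insufficient.

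Three passages sit awkwardly beside this:

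1. The Table 6 rows for Grade 4 thrombocytopenia and Grade 4 febrile neutropenia discontinue everolimus outright. Section 5.7.5 describes Table 6 as general recommendations for patients "while on treatment with RAD001 as single-agent therapy".
2. Section 5.7.2 applies when dosing was omitted for the rest of the previous cycle, or when toxicity newly found on Day 1 delays the new cycle. The new cycle then starts with a "one-level dose reduction of the drug to which the toxicity was attributed". Cytopenias are not excepted.
3. The Table 5 neutropenia row ends by allowing, where neutropenia is the only toxicity calling for a reduction, that "G-CSF may be used and the lenalidomide dose maintained prior to considering dose reduction for Everolimus".

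No text says which instruction prevails.

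**The concern.** Investigators following different passages would treat the same event differently. Myelosuppression is the toxicity to expect: cytopenias lead the lenalidomide adverse event list in Section 5.2.3, and Section 5.2.2 reports dose reductions for myelosuppression in earlier lenalidomide studies.

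Patient safety and consistent handling are at stake first. Interpretation follows. Section 10.2 summarizes exposure by dose level, and Section 10.6 uses responses in the expansion cohorts, including the 3-of-9 rule in adenoid cystic carcinoma, to judge whether the regimen merits a larger trial. If some patients lose everolimus early because of the passage their investigator followed, delivered dose and time on both drugs vary for reasons unrelated to the regimen, and a response is harder to attribute to the combination.

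**Working it through.** The plan states no figure on this point, so there is none to reproduce. The check compares the passages and sizes the dose steps.

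**Step sizes.** Loss = 1 − (mg per 28-day cycle after ÷ mg before). Lenalidomide steps come from Table 3. Everolimus steps come from Table 4, read as a list of dose levels.

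| Drug | Step | mg per cycle | Loss |
|---|---|---|---|
| Lenalidomide | 25 to 20 mg daily | 25×28 = 700 to 20×28 = 560 | 20% |
| Lenalidomide | 20 to 15 mg daily | 560 to 420 | 25% |
| Lenalidomide | 15 to 10 mg daily | 420 to 280 | 33.3% |
| Lenalidomide | 10 mg, days 1–28 to days 1–21 | 280 to 210 | 25% |
| Lenalidomide | 10 to 5 mg, days 1–21 | 210 to 105 | 50% |
| Everolimus | 10 to 5 mg daily | 280 to 140 | 50% |
| Everolimus | 5 mg daily to every other day | 140 to 5×14 = 70 | 50% |
| Everolimus | discontinued | to 0 | 100% |

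**First Grade 4 thrombocytopenia, lenalidomide 25 mg.**

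- Section 5.7.3 with Table 5, whose row covers Grade 3 and above: lenalidomide −20%, everolimus unchanged.
- Section 5.7.2, if the event is attributed to everolimus and dosing was omitted for the rest of the cycle: everolimus −50%, with no lenalidomide step called for. Table 5 acts on the same omission but names lenalidomide whatever the attribution.
- Table 6 row: everolimus −100%. The heading note does not settle this, because it speaks of reduction and not of discontinuation.

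**Grade 4 febrile neutropenia, neutropenia the only toxicity needing a reduction.** The same three outcomes arise. The G-CSF sentence adds a possible fourth: lenalidomide unchanged, with everolimus the next drug considered. This is the only event in which all four readings separate; the G-CSF sentence cannot apply to thrombocytopenia.

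**First Grade 3 thrombocytopenia.** Section 5.7.3, Table 5 and the Table 6 heading note all give lenalidomide first. Only Section 5.7.2 can differ, and only if the event is attributed to everolimus.

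**Can the Grade 4 instructions be combined?** One could lower lenalidomide and stop everolimus together. Section 5.7.3, however, allows continuation on a single drug where a toxicity unique to the other mandates its discontinuation, and Section 5.11 ends treatment for intolerance of either drug. Whether such a patient continues on lenalidomide alone is therefore also unsettled.

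**The case against.** The strongest reply is that the plan already has an order of precedence. This is largely right for dose reductions. The Table 6 row for Grade 3 thrombocytopenia reads "Then resume RAD001 at one dose level lower. If grade 3 thrombocytopenia recurs, discontinue RAD001", and a reader might infer that everolimus is halved at the first such event regardless of lenalidomide. The documents do not support that: the note heading the same table makes everolimus reduction conditional on a lenalidomide reduction that proved insufficient. The note governs the Grade 4 neutropenia and Grade 3 febrile neutropenia reduction rows in the same way. It also shows that Table 6 was partly adapted to the combination, despite the single-agent description in Section 5.7.5.

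Three further replies carry some weight:

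- **Section 5.7.2 is general and Section 5.7.3 specific.** A careful reader may let the specific text win, and attribution will often point to lenalidomide anyway. But the triggers overlap exactly when dosing was omitted for the rest of a cycle, and nothing says that Section 5.7.3 prevails.
- **The G-CSF sentence is permissive and has a consistent reading.** It may mean keeping lenalidomide at its already reduced dose, with G-CSF, before turning to everolimus. That is why it counts here as ambiguous wording and not as a separate rule.
- **The order in Section 5.7.3 concerns reductions, so a discontinuation row need not contradict it.** As a matter of logic this stands. In practice the sequence then has no role at Grade 4, and the plan does not say that this is intended.

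**Conclusion.** The concern holds in limited form. Lenalidomide first is the dominant rule, and the Table 6 reduction rows are subject to it. Two conflicts and one ambiguity remain:

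- At a first Grade 4 thrombocytopenia or Grade 4 febrile neutropenia, everolimus is either kept or ended.
- For a cytopenia attributed to everolimus that leads to omission for the rest of the cycle, the choice is everolimus −50% or lenalidomide −20% from 25 mg (25% to 50% from lower doses).
- In isolated neutropenia, it is unclear which lenalidomide dose is maintained with G-CSF.

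The everolimus percentage assumes that Table 4 lists dose levels; its literal layout is unclear. The documents give no expected frequency of these events under the combination, so the number of patients affected cannot be estimated.

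A reader might also infer that the MTD decision is compromised. The documents do not support that: Sections 5.7.1 and 5.7.3 both send cohort decisions to Table 1. Sample size and power are likewise unaffected. The effect is on delivered dose, time on both drugs and consistent handling of patients, so this should be corrected but is not a flaw in the escalation design.

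**What to change.** The clinical team should reconcile Section 5.7.2, Section 5.7.3, Table 5 and Table 6 as follows:

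1. State one order of precedence for hematologic toxicity, and have Section 5.7.2 either refer to it or say expressly that attribution governs.
2. Say whether the Table 6 Grade 4 discontinuation rows apply to the combination or are single-agent text. If they apply, say whether the patient may continue on lenalidomide alone.
3. Clarify in the Table 5 neutropenia row which lenalidomide dose is maintained with G-CSF.

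Which rule stands is a clinical decision, and this review takes no position on it. The cost is an amendment rewording two tables and the related text in Sections 5.7.2 and 5.7.3. No change to sample size or analysis is needed.
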